- Study duration may be less than or more than 5 years, depending upon the time it takes to accrue the necessary number of confirmed cases.
- The HZ event rates will be monitored on an ongoing basis using the blinded database. If the observed HZ case accrual rate indicates that more than 5 years of patient follow-up will be necessary to accrue the targeted number of confirmed cases, then the SPONSOR will declare the trial infeasible and terminate the study after approximately 5 years of patient follow-up have occurred, from the date the first patient is enrolled.

This study will use an adaptive design based on pre-specified vaccine efficacy criteria, using an independent, external DMC. There will be one interim analysis and one final efficacy analysis. The interim analysis will consist of a futility analysis for each individual subgroup (HM and STM).

The interim (futility) analysis was conducted when at least 50% of the total number of required confirmed HZ cases had accrued in each patient population, HM and STM. The interim analysis was conducted on 29-Oct-2014 for both populations. Results of the analysis were reviewed by the DMC, who made recommendations to the Steering Committee (SC) to end the study in the HM population and continue the STM arm only.

Patients will be monitored for HZ for the entire duration of the study. To that end, patients will be educated on the signs and symptoms of HZ and instructed to call the study site immediately if such symptoms develop, to arrange an evaluation by a medically qualified investigator (medically qualified is defined as physician, or in accordance with local regulations, a nurse practitioner or physician assistant). In addition, monthly efficacy contact by telephone, via the internet, or during a follow-up visit will be required for each patient until study completion, to determine if unreported HZ symptoms occurred.

It is important to note that HZ presentation in immunocompromised patients may be atypical, for instance with cases of rash over several dermatomes. Also, occurrence of severe complications is not uncommon. Finally, visceral involvement is possible and HZ can occur without a rash. In such cases, detection of VZV in diagnostic specimens from blood, cerebrospinal fluid (CSF), lung, liver or other organ may be a key element of the diagnosis of HZ. More information about identification of suspected HZ cases can be found in Section 3.2.17.2.

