To ensure that no alarming, unusual, or unexpected safety problems are occurring with the vaccine in the HM or STM populations, safety will be monitored during the study by the same independent, external DMC that will monitor the interim futility and efficacy analyses. The DMC will periodically evaluate interim safety and efficacy data and will provide periodic recommendations to the SC, to continue, modify, or stop the clinical trial. See section 3.2.21 for more details about the DMC and SC.

Overall, the study may be ended in the following situations:

- 1) When the required number of confirmed HZ cases has accrued; or
- 2) If the decision is made to end the study early following a recommendation made by the DMC based on safety concerns; or
- 3) If the observed HZ case accrual rate indicates that more than 5 years of patient follow-up will be necessary to accrue the targeted number of confirmed cases, then the SPONSOR will declare the trial infeasible and terminate the study after approximately 5 years of patient follow-up have occurred, from the date the first patient is enrolled

In any of these situations, the study will begin to enter the close-out phase, and no additional suspected cases of HZ will be accrued beyond the date for initiation of close-out procedures, as provided in the Close-Out Standard Operating Procedures (SOP) and patients already entered into the suspected HZ-follow-up will complete their 6-month assessment periods. All patients will be contacted to complete the study close-out questionnaire. Details of the close-out procedures will be provided in the Close-Out SOP. In the event the study ends sooner than 1 year after the last vaccine dose is administered, the study will continue to follow all patients for safety and efficacy until all patients have completed 1 year of follow-up.

The clinical, statistical and data management study personnel at the SPONSOR who are involved with study conduct will remain blinded to subject vaccination group allocations until the required number of cases of the primary efficacy endpoint have been observed, study close-out procedures have been completed, data discrepancies have been addressed, and the database is unblinded for the primary efficacy analysis.

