#### 2.7.4 Power and Sample Size

This is an event-driven study. With a 1:1 randomization ratio between the vaccine and placebo groups and a total of 90 HZ cases in the STM population with 2696 patients, the study will have an overall power of ~84.2% to detect  $65\% \text{ VE}_{\text{HZ}}$  at the overall two-sided 0.025 significance level, based on the success criterion of the lower bound 97.5% CI for  $\text{VE}_{\text{HZ}}$  being greater than 25%.

To accrue ~90 confirmed HZ cases in the STM population during the time period from enrollment through approximately the end of maximum 5 years postvaccination, enrollment of approximately 2696 patients (1348 receiving vaccine and 1348 receiving placebo) will be required, assuming 1) 30% total lost-to-follow-up, 2) an HZ rate of 17 per 1000 in the placebo group for STM, 3)  $\text{VE}_{\text{HZ}}=65\%$  for STM, and 4) 36 months of study enrollment. The sample size calculation follows the methods described in Lachin [21].

The dropout rates and the combined HZ event rates will be monitored on an ongoing basis using the blinded database. If ongoing blinded pooled event rate monitoring indicates that there may be fewer than 90 confirmed cases of HZ accrued for the STM population, then the follow-up time may be extended. More specifically, if the observed HZ case accrual rate indicates that more than 5 years of patient follow-up will be necessary to accrue the targeted number of confirmed cases, then the SPONSOR will consider it beyond the adjustment cap and terminate the study after 5 years of patient follow-up have occurred.

A subset of patients will participate in the ELISPOT substudy. Power and sample size of the ELISPOT substudy is discussed in Section 3.5.7.3.

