### 3.1.1.2 Epidemiology of HZ in Patients with STM

Published data of HZ in the STM patient population are much more limited than for other IC populations. HZ incidence in this population was reported to range from 12 to 15 per 1000 person-years [33-39]. Aggressive and prolonged chemotherapy was widely identified as the primary factor for VZV reactivation [33-39]. In the KPNC study, the incidence of HZ among ~12,000 STM patients diagnosed during the study time period was 12 per 1000 person-years [13]. The incidence was 19, 20, and 10 per 1000 person-years in the high, moderate, and low IC groups respectively. The incidence of HZ among patients with breast, prostate, lung and bronchus, colon and melanoma cancer was 15, 10, 21, 8, and 9 per 1000 person-years respectively. When compared with the general population, adjusting for age and gender, STM patients in general had ~2-fold increased risk of the general population while patients currently on chemotherapy or corticosteroid therapy had ~3 fold increased risk. Complications of HZ can be a significant burden to the STM patient. The proportion of HZ cases with PHN was estimated to be as frequently as 8% to 42% [13, 35, 36]. Among the HZ cases in STM patients in the KPNC study, it was shown that ~23% had at least one complication (PHN or any non-pain related complications) [13]. PHN (defined as zoster-associated pain persisting or appearing at or beyond 90 days post-HZ onset) occurred in 8.6% of the patients. Multiple dermatome involvement, skin-related, eye related, and neurological complications occurred in 8.5%, 7.7%, 3.2%, and 0.4% of HZ cases respectively.

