### **3.2.19 Study Completion Procedures**

When the required number of confirmed cases of HZ have accrued, or if the decision is made to terminate the study early following a recommendation made by the DMC based on safety concerns, futile efficacy results from the interim futility analyses, or successful efficacy results from the interim efficacy analysis (see Section 3.5.8.1), the study will begin to enter the close-out phase. If this occurs, the study will continue to allow all patients to complete a minimum of 1 year post-vaccination follow-up for safety and efficacy (including new cases of HZ in these patients). At that time, no additional suspected HZ cases will be accrued, and any patient currently entered into suspected HZ follow-up will complete their 6-month assessment period. All patients must complete at least 1 year of follow-up following the last vaccination prior to completing the study. At the end of the safety follow-up period, all patients will be contacted by telephone to complete the study close-out questionnaire. Data generated from these questions will include any previously unreported symptoms of suspected HZ and SAEs, as well as the patient's final study disposition (e.g., completed, lost to follow-up, death).

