### **3.4.1.2 Post-Vaccination Safety Follow-up**

After the end of the vaccination period (i.e., 28 days postvaccination dose 4), patients will continue to be followed for SAE, regardless of causality, through the end of the study (see Section 3.4.6.1 for additional information on SAEs). Patients will be educated on the criteria for SAE and instructed to call the site immediately if a SAE occurs. In addition, every 3 months (+/- 1 month) beginning 3 months following Visit 5 through the duration of the study, patients will be contacted by study staff either at a scheduled study visit or by telephone, using a pre-specified script, to determine if the patient had a previously unreported clinical adverse experience that met SAE criteria and collect relevant information on SAEs. SAE will be collected as described in Section 3.4.5.1.

In the event the study is terminated sooner than 1 year after the last vaccine dose is administered in this study, the study will continue to allow all patients to complete at least a 1 year post-vaccination safety and efficacy follow-up (including new cases of HZ in these patients).

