### 3.5.5.1.1 Analysis of Vaccine Efficacy on Incidence of HZ Cases

The primary efficacy endpoint is the incidence of HZ in the vaccine and placebo groups in the STM population, defined as the number of HZ cases per 1000 person-years of follow-up from study enrollment to the end of study. Vaccine efficacy for HZ ( $VE_{HZ}$ ) is defined as the relative reduction of the hazard rate of HZ in the V212 group compared with that in the placebo group in STM population. The primary statistical hypothesis for the primary efficacy is  $H_0: VE_{HZ} \leq 25\%$  versus  $H_1: VE_{HZ} > 25\%$ .

To address the primary hypothesis, a Cox proportional hazards regression model in VZV vaccine and placebo recipients stratified by age (< 50 years of age versus  $\geq 50$  years of age based on a MITT population as described in section 3.5.4.1) will be used as the primary analysis to compare the incidence of HZ between the vaccine and placebo groups. The study time period in the primary analysis will be from the enrollment to the stop date of HZ surveillance. Patients who do not develop HZ will be censored at the stop date of HZ surveillance. The follow-up time for patients who develop HZ will be from the enrollment to their HZ onset date. For the interim analysis, this stop date will be the corresponding database cutoff date for the analysis. Efron's method will be used to handle ties in event times.

A key supportive analysis will include calculation of  $VE_{HZ}$  using a PP population as described in section 3.5.4.1 based on Cox proportional hazards regression model. The study time period in the primary analysis will be from the date of Dose 4 to the stop date of HZ surveillance. The model and covariate adjustment will be similar to that noted in the MITT approach. In addition, incidence of HZ and  $VE_{HZ}$  will also be summarized by age group (50 to 59, 60 to 69, and 70+) as exploratory analyses.

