### 3.5.5.1.2 Analysis of Vaccine Efficacy on Secondary Efficacy Endpoints

Three secondary efficacy endpoints are defined for the STM population and in the HM population on an exploratory basis.

Since the incidences of moderate to severe HZ-associated pain, HZ-complications as defined by the composite endpoint, and PHN are unknown in this population, formal hypothesis testing for these secondary endpoints will not be performed. The incidence of the secondary efficacy endpoints of moderate to severe HZ-associated pain, composite complication endpoint, and the incidence of PHN, defined as pain in the area of the HZ rash with a “worst pain in the last 24 hours” score of 3 or greater (on a 0 to 10 scale) on the ZBPI that persists or appears greater than or equal to 90 days after HZ onset, (point estimate and 95% CI) will be compared between vaccine and placebo groups using Cox proportional hazards regression stratified by age (< 50 years of age versus  $\geq$  50 years of age) based on the MITT population. For patients who develop PHN, the PHN event onset will be the date of HZ rash onset. Patients who do not develop PHN will be considered as censored at the stop date of their HZ surveillance. Furthermore, the count and proportion of each component of the secondary efficacy composite endpoint among all randomized patients in the vaccine and placebo groups will be summarized.

Sensitivity analyses for vaccine efficacy on PHN based on alternative definitions [pain in the area of the HZ rash with a “worst pain in the last 24 hours” score of 3 or greater (on a 0 to 10 scale) on the ZBPI that persists or appears more than 30, 60, 120, and 180 days after HZ rash onset] will be compared between the vaccine and placebo groups in the MITT population.

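### Does the loosely defined stop date of HZ surveillance leave the primary censoring rule open?

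*Combined protocol and SAP*

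**What the plan says.** For the primary analysis, Section 3.5.5.1.1 runs time from enrolment to zoster onset or to the end of surveillance: "Patients who do not develop HZ will be censored at the stop date of HZ surveillance". For the interim only, it equates that date with the database cutoff. The same section defines incidence per 1000 person-years of follow-up to the end of the study.

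Other sections bear on when surveillance ends:

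- Section 2.4.1, on close-out: "no additional suspected cases of HZ will be accrued beyond the date for initiation of close-out procedures", with the details left to a Close-Out SOP. It then keeps all patients under safety and efficacy follow-up to 1 year if the study ends sooner than that after the last dose.
- Section 3.2.19 lets patients "complete a minimum of 1 year post-vaccination follow-up for safety and efficacy (including new cases of HZ in these patients", and only then says that accrual of suspected cases stops at that time.
- Section 3.4.1.2 lets patients, after early termination, "complete at least a 1 year post-vaccination safety and efficacy follow-up (including new cases of HZ in these patients".
- Section 2.4.1, on monitoring: "Patients will be monitored for HZ for the entire duration of the study".
- Section 3.5.5.1.2, on PHN: "Patients who do not develop PHN will be considered as censored at the stop date of their HZ surveillance".
- Section 2.7.4 sizes the study "assuming 1) 30% total lost-to-follow-up".

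**The concern.** There are two gaps. The first is at patient level. Read literally, one study-wide date would keep patients who died or were lost in the risk set after anyone could have observed zoster in them. That would lower the absolute rates in both arms and, if loss differed by arm, would shift VE.

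The second is at study level. If the 90th case arrives while some patients are still within 1 year of their last dose, one sentence stops case accrual at the start of close-out and two others go on counting new cases. The primary event set would then depend on which text is followed. Section 3.5 says no separate SAP will be issued, so nothing later is promised to settle it. Leaving the cut open in a trial judged on about 90 events looks like a choice that should have been made in advance.

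**Working it through.** **Inputs.** N = 2696 randomised 1:1 (1348 per arm), 36 months of enrolment, 30% total loss, 17 per 1000 in placebo, VE 65%, 90 cases (Sections 2.7.4 and 3.5.7.1). My assumptions: uniform entry, exponential zoster and loss times, and the 30% loss reached by 5 years (η = −ln 0.7 / 5 = 0.0713 per year) or by 3.5 years, the mean follow-up at month 60 (η = −ln 0.7 / 3.5 = 0.1019).

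**Stated power, reproduced.** Conditional on 90 cases, the vaccine share is 0.75/1.75 at VE 25% and 0.35/1.35 at VE 65%. The largest vaccine count significant at one-sided 0.0125 is 27 (attained 0.0083). P(at most 27) at VE 65% is 84.2%, as the plan states. Censoring dates do not enter this calculation.

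**Patient level.** With h = λ + η, R = 3 years and analysis at T ≥ R, expected cases per arm are

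E = 1348 × (λ/h) × {1 − [exp(−h(T−R)) − exp(−hT)] / (hR)}.

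At T = 5 and η = 0.0713:

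- Placebo: λ = 0.017, h = 0.0883, so E = 1348 × 0.1925 × {1 − (0.8381 − 0.6430)/0.2650} = 68.4.
- Vaccine: λ = 0.017 × 0.35 = 0.00595, h = 0.0773, so E = 24.4.
- The total, before rounding, is 92.9. With η = 0.1019 it is 88.1. With no loss it is 105.5.

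The plan's figure of about 90 appears only when lost patients stop contributing. The PHN text ties the date to each patient's own surveillance, and person-years of follow-up cannot sensibly include time after death or loss. The dates exist: contact is monthly (Section 1.7), final-visit activities are done at discontinuation (Section 3.2.20), and final disposition is recorded (Section 3.2.19).

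**Study level.** Doses are about 30 days apart, so the last patient's dose 4 falls near month 36 + 3 to 4 = 39 to 40, and the 1-year point near month 51 to 52. The texts diverge only if the 90th case comes earlier. Setting total E = 90 and solving for T (each range covers the two loss patterns):

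| Placebo rate per 1000 | True VE | Month of 90th case |
|---|---|---|
| 17 | 65% | 58.5–61.1 |
| 17 | 50% | 54.0–56.0 |
| 17 | 25% | 48.3–49.8 |
| 15 | 25% | 52.8–54.6 |
| 12 | 25% | 62.6–65.7 |
| 20 | 50% | 48.1–49.5 |
| 20 | 25% | 43.5–44.5 |

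The 12 to 15 range is the published solid-tumour range in Section 3.1.1.2. The 20 is the moderate group in the same section: "The incidence was 19, 20, and 10 per 1000 person-years in the high, moderate, and low IC groups respectively".

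**Cases affected where the texts diverge.** If every patient is followed to month 51 or 52, the extra cases are E(51 or 52) − 90: 3 to 10 at 17 per 1000 and VE 25%, 4 to 10 at 20 and VE 50%, 19 to 27 at 20 and VE 25%. If only patients short of 1 year continue, each to his or her own 1-year point, these become about 0.1–0.6, 0.1–0.6 and 2.0–3.6.

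**Effect on the test.** The critical count moves with the total. At 104 cases it is at most 32 in the vaccine arm (attained 0.0077), against 27 of 90 (0.0083). Either cut keeps the one-sided error below 0.0125.

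**The case for a change.** The strongest case for a change is that this protocol text is the whole analysis specification and that the conflict binds when cases arrive fast. That includes the null VE of 25% at the plan's own rate, where up to about 10 cases could fall between the two dates against a boundary of 27 vaccine cases in 90. A written rule would cost a few sentences, use data already collected and remove any later choice.

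The ambiguity is real, and the wording could be tidier. The consequence is not shown. Section 2.4.1 keeps the sponsor's study personnel blinded until close-out is complete and data queries are resolved, so the cut is fixed without knowledge of the case split. Sections 2.4.1, 3.2.19 and 3.4.1.2 can be read together as a rule with an exception: accrual stops at close-out, except that patients short of 1 year are followed, with their cases, until they reach it. The operational date is left to the Close-Out SOP, which is not among the documents. Section 1.4 asks for at least 90 cases, so a total above 90 is already allowed for. The statement that patients are monitored throughout the study sets no competing date.

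**Conclusion.** No change is needed. At patient level, the plan's endpoint definition, its PHN wording and its case projection all point to censoring at each patient's own last surveillance, and an analyst would do that unprompted. At study level, the texts diverge only if the 90th case precedes about month 51 to 52. That is not expected at 17 per 1000 with VE of 50% to 65%, nor at 12 to 15 per 1000 even with VE 25%. It would happen at 17 per 1000 with VE 25%, or at 20 per 1000 with VE of 50% or less. In those cases the extra events number from under 1 to 27, depending on scenario and reading, and they are counted under the same rule in both blinded arms, with no bias shown.

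The stated power of 84.2%, the 2696 patients, the 90 cases and the one-sided 0.0125 all stand. The timing rests on uniform 36-month entry, exponential loss reaching 30% by 3.5 or 5 years, and last doses at month 39 to 40. Naming the date would be good housekeeping, but it would record what the analysis would do anyway.

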## **1.5 SAMPLE**

This study will enroll men and women with a life expectancy of at least 12 months, who are varicella-history (or VZV-antibody) positive or based on regional epidemiology have a high likelihood of latent VZV infection, are not likely to undergo hematopoietic cell transplant (HCT) and

- are 18 years of age or older and receiving chemotherapy for STM or HM.

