The results of HZ case determination (PCR versus case adjudication by the CAC) will be summarized by vaccination group. The probability of developing HZ will be estimated and displayed by the Kaplan-Meier method. The incidence rates of HZ post randomization (enrollment) in each group will be compared by the nonparametric log-rank statistic without covariate adjustment. Also, the incidence of HZ will be summarized by vaccination group in terms of number of cases per 1000 person-years in those patients who only received a total of 1 dose, 2 doses, and 3 doses of vaccine/placebo using the MITT population if a sizable proportion (>10%) is observed in each category (1 dose, 2 doses, and 3 doses).

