The rate of SAEs, vaccine-related SAEs and death that occur throughout the entire study follow-up period will also be summarized per 1000 person-years of follow-up by vaccination group, to account for potential differential follow-up time by vaccination group. The probability of mortality will also be estimated and displayed by the Kaplan-Meier curve for each vaccination group. Risk difference and the corresponding 95% CI of these long-term safety parameters between the vaccine group and placebo group will be provided using an asymptotic method for differences of 2 independent Poisson rates. Mortality and SAEs, including vaccine-related SAEs will also be listed by patient with more detailed information.

SAEs and Tier-1 adverse experiences during the primary safety follow-up period will be summarized by body system.

Summaries of varicella/varicella-like or an HZ/HZ-like rash occurring during the primary safety period, through 28 days postvaccination 4, will be provided by vaccination group and by lesion type (wild type versus vaccine strain) determined by PCR. Occurrence of opportunistic infections during the primary safety period (from Day 1 to Day 28 Postdose 4) will also be summarized as adverse experiences. Occurrence of opportunistic infections and recurrence of disease that are SAEs at any time during the study will also be summarized.

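### The probability of developing HZ is to be shown by Kaplan-Meier, and the plan does not say how deaths enter; if patients are censored at death, the curve overstates that probability

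*Combined protocol and SAP*

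**What the plan says.** Section 3.5.5.1.1 makes a stratified Cox model the primary analysis. Vaccine efficacy "is defined as the relative reduction of the hazard rate of HZ in the V212 group compared with that in the placebo group". The same section then adds a descriptive display: "The probability of developing HZ will be estimated and displayed by the Kaplan-Meier method". An unadjusted log-rank comparison goes with it.

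The censoring rule in that section is "Patients who do not develop HZ will be censored at the stop date of HZ surveillance". Death is not mentioned. For the interim analysis the section adds that "this stop date will be the corresponding database cutoff date for the analysis", which is one calendar date for everyone. Section 3.5.5.1.2 words the rule for PHN per patient: "Patients who do not develop PHN will be considered as censored at the stop date of their HZ surveillance".

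Deaths are recorded. Close-out data under Section 3.2.19 include "the patient's final study disposition (e.g., completed, lost to follow-up, death", and Section 3.4.5.1 requires death from any cause to be reported throughout the study. Section 3.5.5.3 plans a mortality curve by group: "The probability of mortality will also be estimated and displayed by the Kaplan-Meier curve for each vaccination group". No section links death to the HZ follow-up time, and none names a cumulative-incidence or competing-risk method.

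**The concern.** A patient who has died can no longer develop HZ. When death is treated as ordinary censoring, Kaplan-Meier assigns that patient the same future HZ risk as those still alive. The result is a net risk, in a hypothetical setting without death. It is not the proportion of patients who will develop HZ, which is what the sentence in Section 3.5.5.1.1 says will be shown.

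Deaths during follow-up are foreseeable. Section 1.5 enrolls "men and women with a life expectancy of at least 12 months", the STM patients are on chemotherapy, and Section 2.4.1 lets the study run to about 5 years from the first enrollment. This curve is the plan's only estimate of the cumulative probability of HZ. A reader who takes an absolute risk or a risk difference from it would get figures that are too high.

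**Working it through.** **Inputs.** From Section 3.5.7.1: placebo HZ rate 17 per 1000 (read as person-years, h = 0.017 per year), VE 65% (vaccine h = 0.017 × 0.35 = 0.00595), 30% total loss to follow-up, 36 months of enrollment, 1348 patients per group and about 90 cases. From Section 2.4.1: a limit of about 5 years from the first patient enrolled. The death hazard m is an assumption, because the documents give none.

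**Check of the inputs against the plan's own target.** The plan gives no figure for the probability of HZ, but its case target can be checked. With uniform enrollment over 3 years and a study length of 5 years, potential follow-up runs from 2 to 5 years. With loss hazard η = −ln(0.70)/5 = 0.0713 and s = h + η, expected cases per group are

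1348 × (h/s) × [1 − (e^(−2s) − e^(−5s))/(3s)].

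This gives about 68.4 (placebo) and 24.4 (vaccine), 92.9 in all. If the 30% loss is reached over 3.5 years instead (η = 0.1019), the total is 88.1. Both agree with about 90, which supports reading the rate as person-years and follow-up as 2 to 5 years.

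**Formulas for the point**, with constant hazards:
- One minus Kaplan-Meier, death censored at its date: 1 − e^(−ht)
- Cumulative incidence, death competing: h/(h+m) × (1 − e^(−(h+m)t))

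**5 years, all of the 30% loss taken as deaths** (m = −ln(0.70)/5 = 0.0713):
- Placebo by Kaplan-Meier: 1 − e^(−0.085) = 8.15%
- Placebo by cumulative incidence: (0.017/0.0883) × (1 − e^(−0.4417)) = 6.87%. The gap is 1.28 points, about 19% relative.
- Vaccine: 2.93% against 2.47%
- Risk difference: 5.22 against 4.40 points
- Relative reduction: 64.0% against 64.1%

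**5 years, smaller shares dead by year 5:**

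| Dead by 5 years | Placebo KM | Placebo cumulative incidence | Risk difference, KM | Risk difference, cumulative incidence |
|---|---|---|---|---|
| 10% | 8.15% | 7.74% | 5.22 | 4.96 |
| 20% | 8.15% | 7.32% | 5.22 | 4.69 |
| 30% | 8.15% | 6.87% | 5.22 | 4.40 |

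**2 years**, which all patients could reach under the 5-year limit. Placebo by Kaplan-Meier is 1 − e^(−0.034) = 3.34%. Cumulative incidence at m = 0.05, 0.10 and 0.15 per year is 3.18%, 3.03% and 2.89%, a gap of 0.2 to 0.5 points.

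**Dependence on the censoring rule.** A simulation of 200,000 patients at the placebo rate, with the 30% death assumption and administrative censoring spread over 2 to 5 years, was read at 4.9 years:
- Deaths censored at the date of death: one minus Kaplan-Meier 8.05%, Aalen-Johansen 6.81%
- Deaths kept in the risk set until the common stop date: one minus Kaplan-Meier 6.81%, so the overstatement disappears

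**The case against.** The strongest reply is that the plan never says deaths are censored at death. A reader might infer that it does, but Section 3.5.5.1.1 speaks only of a stop date of surveillance. Read literally as one common date, the dead stay in the risk set and Kaplan-Meier equals the cumulative incidence. This stands as far as it goes: censoring at death is an inference. It is still the natural reading, because the PHN rule is worded per patient and the common-date reading would count time after death as person-years of follow-up. Two readings that give different curves also show that the rule needs stating.

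Several stronger inferences are tempting, and the documents do not support them:
- **That the efficacy result is biased.** Success rests on the Cox lower bound. With follow-up ended at death, Cox, log-rank and person-year rates do not use one minus Kaplan-Meier.
- **That this is the only absolute measure of HZ.** Cases per 1000 person-years are planned by group, and incidence is also summarized by 6-month interval.
- **That a planned number needed to vaccinate would be wrong.** Neither that number nor an absolute risk reduction is a planned output.
- **That the gap is much larger.** Death rates of 10 or 15% per year mean 39% or 53% dead by year 5 (1 − e^(−0.5), 1 − e^(−0.75)). Both exceed the plan's only attrition figure, and most patients would have less than 5 years of follow-up.
- **That the mortality curve in Section 3.5.5.3 repeats the error.** Kaplan-Meier is sound for death from any cause, and planning it states no expected rate.

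It is also fair to say that Kaplan-Meier is the usual companion to a hazard-based analysis, and Table 3-2 names it for durability. That argues against removing it, but not for calling it the probability of developing HZ.

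**Conclusion.** The point holds in a limited form. The plan leaves the handling of deaths in this estimate unstated. Under the natural reading, the method overstates the quantity it is said to estimate. The direction is certain once deaths are censored at death; the size is not, because no mortality rate is given and the 30% loss is not split by cause. Taking all of that loss as deaths, the 5-year placebo overstatement is 1.28 points (8.15% against 6.87%). At 2 years it is 0.2 to 0.5 points for deaths at 5 to 15% per year. These figures assume constant hazards and equal mortality in the two groups. Under the same assumptions the relative reduction stays near 64%. The effect is confined to absolute risks read from a descriptive curve; alpha, power and the primary conclusion are untouched. It is a minor point with a free remedy.

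**What to change.** In Section 3.5.5.1.1:
- Report the probability of HZ by vaccination group as the Aalen-Johansen cumulative incidence, with death before HZ as a competing event.
- State that patients who die without HZ end HZ follow-up at the date of death. This also settles the follow-up time for the Cox model and the person-year rates.
- Keep the Cox model for vaccine efficacy. If the Kaplan-Meier curve is kept beside the cumulative incidence, label it as HZ risk in the absence of death.

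Section 3.5.5.3 needs no change. The cost is two or three sentences and a standard procedure. Deaths are already collected, and sample size, alpha and study conduct do not change.
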